To evaluate the efficacy of the injections of 400 units of the product at Week 6 (finger/ wrist flexors: 240 units, elbow flexors: 160 units), comparing to that of 240 units (finger/ wrist flexors: 240 units, elbow flexors: placebo).	The responder rate: The rate of the subjects that Modified Ashworth Scale (MAS) score was reduced at least 1 from baseline in the elbow flexors.
Secondary	
To evaluate the efficacy of 400 units of the product, comparing to 240 units of the product	
 • The responder rate of MAS score from baseline in the finger, thumb and wrist flexors • Changes in MAS score from baseline in the finger, thumb, wrist and elbow flexors • Changes in Disability Assessment Scale (DAS) from baseline
To evaluate the safety and tolerability of the product of 400 units, comparing to 240 units of the product/ To evaluate the safety and tolerability of 400 units of the product	
 • Adverse events • Physical examinations • Clinical laboratory tests (haematology, blood biochemistry, urinalysis) • Vital signs (heart rate, blood pressure, body temperature)
Exploratory	
To evaluate the efficacy of 400 units of the product	
 • Changes in MAS score from baseline in finger, thumb, wrist, elbow, pronation of the forearm and shoulder flexors
To evaluate the other efficacy of the product of 400 units, comparing to 240 units of the product/ To evaluate the other efficacy of 400 units of the product	
 • Changes in Numeric Rating Scale (NRS) for pain from baseline • Changes in other items of DAS from baseline • Clinical Global Impression of Change (CGI) of functional disability by an investigator • CGI of functional disability by a patient • Time to patient-reported onset of spasticity symptom relief • Patient-reported benefit of injection • Time to qualification for retreatment
To evaluate neutralizing antibody production	
 • Testing for neutralizing antibody

Overall Design:

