6.1.2. Day 1 (prior to injection)

Subjects eligible for enrolment in the study must meet all of the following criteria on Day 1 (prior to injection):

Subjects and Characteristics of the Disease

31. Patients who meet the following criteria on MAS score: (Test position : sitting)
- At least 3 in the elbow flexors
- And
- At least 2 in the finger or wrist flexors

Preceding Treatments and Concomitant Medications/Therapies

32. If centrally acting muscle relaxants, tetracycline antibiotics, anticholinergics, benzodiazepines, or benzamides are given, the dose and regimen must be stable at least for the last 2 months before Day 1; Patients who can maintain the same dosage and regimens at least in the blind phase after initial injection (dose reductions and discontinuation of the drugs are acceptable in the open-label phase. However, second dose increase, resumption, and or new treatment will not be performed).
33. If intrathecal baclofen is given, the dose and regimen must be stable at least for the last 1 month before Day 1; Patients who can maintain the same dosage and regimens at least in the blind phase after initial injection (intravenous bolus is not acceptable, dose reductions and discontinuation of the drugs are acceptable. However, second dose increase, resumption, and or new treatment will not be performed).
34. If antiepileptic agents are given, the dose and regimen must be stable at least for the 1 month before Day 1; Patients who can maintain the same dose and regimens at least in the blind phase after initial injection (dose reductions and discontinuation of the drugs are acceptable in the open-label phase. However, second dose increase, resumption, and new treatment will not be performed).
35. If a physical therapy, occupational therapy, or a static splint on the study involvement upper limbs is given, the frequency and treatment regimen must be stable at least for the last 3 weeks before Day 1; Patients who can maintain the same dose and regimens at least in blind phase (In the open-label phase, the frequency and treatment regimen can be changed depending on the condition of spasticity).

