7.1. Treatments Administered

Study Treatment Name:	GSK1358820 (Nonproprietary name: Botulinum toxin type A)	Placebo
Dosage formulation:	Injection	Injection
Ingredient and quantity (Per vial)	Botulinum toxin A 100 units Sodium chloride 0.9 mg Human serum albumin 0.5 mg	Sodium chloride 0.9 mg
Packaging and Labeling	It will be listed on the labelling in accordance with the regulatory requirements in Japan.	It will be listed on the labelling in accordance with the regulatory requirements in Japan.
Manufacturer	Allergan (Ireland)	Allergan (Ireland)
Dose	400 units	240 units
Dosing instructions	
Part 1: 240 or 400 units of the product will be injected into the muscles that act on the finger (including thumb flexors), wrist and elbow flexors, in accordance with Table 2. In and after Part 2: 400 units of the product will be injected into the muscles that act on the finger (including thumb flexors), wrist, elbow and shoulder flexors in accordance with Table 3. For the muscles that the investigator considers unnecessary to be treated, an injection may be skipped. Dose intervals should be at least 12 weeks.
 
For adjustment of the product, the product will be dissolved with 2 ml of normal saline per 1 vial (100 units). The details will be described on Table 4.
	

In the blind phase

- A total of 240 units of product will be injected into the muscles that act on finger (including thumb flexors) and wrist flexors, and a total of 160 units of the product or placebo for the muscles that act on the elbow flexors in divided doses in accordance with [Table 2](#).
- The muscles which are not listed on [Table 2](#) must not be used.
- All of the muscles described on [Table 2](#) must be used. If the subject with no symptoms with thumb, the investigator does not have to inject to thumb.
- If the total dose for the muscles that act on the finger and wrists flexors is ensured by 240 units, and 160 units for the muscles that act on the elbow flexors, the dose can be adjusted at an investigator's discretion based on the symptoms of a subject.

In the open-label phase

- The investigator will decide the dose and the muscle to be injected based on the symptoms of patients, and a total of 400 units will be injected in divided doses. For the muscles that the investigator considers unnecessary to be treated, an injection may be skipped.

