The subject's wrist, fingers, thumb and elbow should all be evaluated during the blinded period. Likewise, the subject's wrist, fingers, thumb and elbow should all be evaluated for MAS at Visit 5 and QRV of the blinded period. Subjects meeting the eligibility and transferred to the open-label period should be evaluated for MAS at Visit 1 of Treatment Period 2 on the same day; provided that measurement may be performed only once if the affected part to be evaluated is the same. Meanwhile, MAS needs to be evaluated again if the affected part to be evaluated is not the same. In subjects who have received no injection to any muscles affecting the thumb, MAS measurement on the thumb will not be performed.

- MAS measurement during the open-label period

During the open-label period, MAS should be evaluated for the flexors at which the muscle given the study treatment functions (fingers, thumb, wrist, elbow, fore-arm) (Table 6). If the subject is determined to be eligible, the V5/QRV and V1 would be on the same day, and therefore, the MAS

measured at V5/QRV of the previous treatment period should not be measured again on V1; the measurement on V5/QRV should be used for the assessment (Figure 6). MAS on flexors to be newly assessed on V1 should be evaluated before dose on V1. The MAS on the shoulder should be evaluated comprehensively for the adductor and invertor.

Table 6 Regions to be evaluated for MAS during the open-label period

Number	Muscles to be injected	Regions to be evaluated for MAS
A1	Biceps brachii	Elbow flexors (flexion)
A2	Brachialis	
A3	Brachioradialis	
B1	Flexor carpi radialis	Wrist flexors (flexion)
B2	Flexor carpi ulnaris	
C1	Flexor digitorum profundus	Fingers (flexion)
C2	Flexor digitorum superficialis	
C3	Lumbricales interossei	
D1	Flexor pollicis longus	Thumb (flexion, adduction)
D2	Adductor pollicis	
D3	Opponens pollicis	
E1	Pronator teres	Forearm (pronate)
E2	Pronator quadratus	
F1	Teres major	Shoulder (flexion, adduction, and internal rotation)
F2	Latissimus dorsi	
F3	Pectoralis major	
F4	Subscapularis	

Visit	SV	Part 1					Part 2					Part 3					Part 4					
		V1	V2	V3	V4	V5	V1	V2	V3	V4	V5	V1	V2	V3	V4	V5	V1	V2	V3	V4	V5	
A.Elbow	●	●	●	●	●	●	(○)	●	●	●	●	(○)	●	●	●	●	(○)	●	●	●	●	
B.Wrist	●	●	●	●	●	●							●	●	●	●	●	(○)	●	●	●	●
C.Finger	●	●	●	●	●	●	(○)	●	●	●	●	(○)	●	●	●	●	(○)	●	●	●	●	
D.Thumb		●	●	●	●	●																
E.Forearm							●	●	●	●	●	(○)	●	●	●	●	(○)	●	●	●	●	
F.Shoulder							●	●	●	●	●						●	●	●	●	●	

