10.3. Statistical Analyses

10.3.1. Efficacy Analyses

This study is not intended to verify a statistical hypothesis; thus, there will be no statistical test.

All of the efficacy analyses will be performed on the ITT population separately for the blinded period and the open-label period.

Endpoints	Statistical Analysis Methods
Primary	
The primary endpoint is the proportion of subjects whose MAS score on the elbow at Week 6 of the initial dose decreased by at least 1 level from the baseline (responder rate). The primary endpoint will be calculated as the proportion of subjects whose MAS score decreased by at least 1 level from the baseline in the ITT population. Also, a 95% confidence interval of the intergroup difference in the responder rate will be computed. Subjects with no MAS score available at Week 6 will not be counted as subjects whose MAS score decreased by at least 1 level from the baseline (that is, counted in as non-responder).
 
The MAS scores, 0, 1, 1+, 2, 3, and 4 will be encoded to 0, 1, 2, 3, 4, and 5, respectively, for the analysis purpose.

Secondary	
Unless specified otherwise, the data up to Week 12 of treatment will be summarized for each repeated dose during the open-label period.
 
During the blinded period, a mixed model for repeated measurement (MMRM) will be used for the analysis on the endpoints specified below, and the least-square mean and 95% confidence interval will be calculated. The details of the model will be described in the statistical analysis plan. For the open-label period, only a summary statistics will be performed for each treatment group. Missing values will not be imputed.
 
 · Change in MAS score in the fingers, thumb, wrist, and elbow from the baseline · Change in Disability Assessment Scale (primary endpoint) from the baseline 
The proportion of subjects in whom MAS score in the fingers, thumb, wrist, and elbow decreased by at least 1 level from the baseline (responder rate) during the blinded period will be analyzed with the same method as that for the primary endpoint. For the open-label period, the denominator to be used for the calculation of responder rate shall be the number of subjects in each subgroup stratified by the number of injections given, not the ITT population. Also, a 95% confidence interval of the intergroup difference in the responder rate will not be calculated.

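### The blind-phase thumb responder rate counts thumbs that were deliberately left untreated and unscored as treatment failures

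*Protocol*

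**What the plan says.** The synopsis lists as a secondary endpoint "The responder rate of MAS score from baseline in the finger, thumb and wrist flexors".

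On treatment in the blind phase, 7.1 requires all the muscles in Table 2 to be used, with one exception: "If the subject with no symptoms with thumb, the investigator does not have to inject to thumb".

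On measurement in the blind phase, 9.1.1.1 says: "In subjects who have received no injection to any muscles affecting the thumb, MAS measurement on the thumb will not be performed".

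On analysis, 10.3.1 says that the blind-phase responder rates for fingers, thumb, wrist and elbow "will be analyzed with the same method as that for the primary endpoint". The primary method has two parts:

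- The rate is "the proportion of subjects whose MAS score decreased by at least 1 level from the baseline in the ITT population".
- The missing-data rule is: "Subjects with no MAS score available at Week 6 will not be counted as subjects whose MAS score decreased by at least 1 level". The text adds that they count as non-responders.

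Section 10.2 admits to the ITT population any randomised subject with at least one post-baseline efficacy assessment. It does not ask for an assessment of a particular joint.

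**The concern.** Counting a missing score as non-response is a defensible conservative rule when the score was due and was not obtained. Here it also captures scores that the protocol itself says are not to be taken. A subject with a symptom-free, untreated thumb has nothing to respond to and no thumb assessment, yet enters the thumb rate as a failure. The reported rate then mixes two quantities: how often treated thumbs improve, and how often investigators choose to treat the thumb. A reader of the study report could not separate them. Section 10.3.1 also calls for a 95% confidence interval for the between-arm difference in this rate, so the artefact would carry into that interval.

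**Working it through.** **The plan's own figures.** Section 10.1 gives power of about 62% and a probability of at least 98% that the 400-unit rate exceeds the 240-unit rate, for 70% against 50% elbow responders with 60 per arm and two-sided 5%.

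- SE = sqrt(0.70 x 0.30/60 + 0.50 x 0.50/60) = 0.0876, and 0.20/0.0876 = 2.28.
- Power: 62.7% (unpooled normal), 61.1% (pooled normal), 61.8% (exact, uncorrected chi-square).
- Probability of exceeding: 98.9% (normal), 98.5% (exact binomial).

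Both figures reproduce. They concern the elbow, and nothing below changes them.

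**Does the plan exempt unscored thumbs anywhere?**

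1. An uninjected thumb has no Week 6 score by design (7.1 with 9.1.1.1).
2. The subject stays in the ITT population through any other post-baseline efficacy assessment (10.2).
3. The only special denominator in 10.3.1 is for the open-label period, by number of injections given.
4. The statement in 10.3.1 that missing values are not imputed stands in the paragraph on the repeated-measures change endpoints and the open-label summaries. It does not override the responder rule.

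So no sentence removes these thumbs from the blind-phase rate.

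**Effect on each arm's rate.** Let p be the true responder rate among injected thumbs and f the share not injected. The reported rate is p x (1 - f) + 0 x f = p(1 - f). Neither p nor f is in the protocol. Here p = 60% is an illustration and f = 5% to 30% is an assumption. The last two columns give the 95% confidence interval half-width for a between-arm difference when both arms have the same true 60%, starting from 60 ITT subjects per arm.

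| f | Thumbs scored per arm | Reported rate | Half-width as written (n = 60) | Half-width, injected thumbs only |
|---|---|---|---|---|
| 5% | 57 | 57% | 17.7 points | 18.0 points |
| 10% | 54 | 54% | 17.8 points | 18.5 points |
| 20% | 48 | 48% | 17.9 points | 19.6 points |
| 30% | 42 | 42% | 17.7 points | 21.0 points |

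Example at f = 20%, as written: 1.96 x sqrt(2 x 0.48 x 0.52/60) = 0.179. Injected thumbs only: 1.96 x sqrt(2 x 0.60 x 0.40/48) = 0.196.

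**Effect on the difference.** The reported difference is p1(1 - f1) - p2(1 - f2).

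- Equal f: the true difference is multiplied by (1 - f). For 60% against 50% and f = 20%, this gives 48% - 40% = 8 points instead of 10.
- No true difference and equal f: the reported difference is also zero in expectation.
- No true difference and unequal f: for 60% in both arms with f = 10% and 20%, this gives 54% - 48% = 6 points that do not exist.

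**The case against.** Several points on the other side carry weight.

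**The share f may be small.** Inclusion criterion 3 in 6.1.1 asks for spastic symptoms in the finger, including the thumb, as well as in the wrist and elbow. Read strictly, few subjects would have a symptom-free thumb. This limits the size but does not remove the conflict, because 7.1 and 9.1.1.1 both provide expressly for such subjects.

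**A reader might infer that the treatment comparison is materially diluted.** The design does not support that. Both arms receive the same 240 units in the finger, thumb and wrist muscles, and only the elbow differs. The expected thumb difference is therefore near zero, and there is little to dilute. The thumb exemption is the same in both arms and the phase is blinded, so f should be similar in the two arms apart from chance.

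**A reader might also infer that finger and wrist rates suffer the same fault.** The Day 1 criterion asks for "At least 2 in the finger or wrist flexors", so one of the two might seem able to start at 0 with no room to improve. But criterion 3 asks for symptoms in both, 7.1 exempts only the thumb from injection, and 9.1.1.1 requires fingers and wrist to be scored. Neither joint is left unmeasured by design, and a joint with no spasticity at entry would sit badly with criterion 3.

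**The SAP could set the denominator.** It was not at hand. But 10.3.1 defers the repeated-measures model details to the SAP while fixing the responder method itself, so a different denominator there would depart from the protocol.

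**Conclusion.** The conflict is real and follows from the protocol text alone: carried out as written, 10.3.1 gives a wrong thumb responder rate in each arm. The rate is understated by the factor (1 - f). With f assumed at 5% to 30%, a true 60% becomes 57% to 42%; the actual size is unknown because the protocol gives no f. Any true between-arm difference shrinks by the same factor if f is equal, and unequal f can produce a spurious one, but no thumb difference is expected from the design.

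It would be too strong to say that the trial's conclusion is at risk. The thumb rate is a secondary endpoint, 10.3.1 plans no statistical test, and the criterion for a positive result in 5.1 rests on the elbow point estimate alone. The point is minor but should be fixed.

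**What to change.** In 10.3.1, state that the blind-phase thumb responder rate uses as denominator the ITT subjects whose thumb muscles were injected in Part 1. Within that set, keep the rule that a missing score counts as non-response, so that it applies only to thumbs that were due for measurement and were missed. Report the number of subjects excluded in each arm, so that any imbalance in f is visible. Leave the finger, wrist and elbow analyses as they are.

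Separately, reconcile inclusion criterion 3 in 6.1.1, which names thumb symptoms, with the provision in 7.1 for subjects who have none.

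The cost is one sentence in 10.3.1, carried into the SAP, and a somewhat smaller thumb denominator. At f = 20% the illustrative half-width for the difference goes from 17.9 to 19.6 points. The narrower figure comes from counting thumbs that were never assessed.

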9.1.1.5. Clinical Global Impression of Change (CGI) assessed by a patient

According to "2. SCHEDULE OF ACTIVITIES (SoA)" the investigator (or subinvestigator) will use Table 9 to record subject-reported CGI. The investigator shall interview each subject on changes in spasticity from predose, and the subject will evaluate it using Table 9.

9.1.1.6. Time to patient-reported onset of spasticity symptom relief (Visit 2):

According to "2. SCHEDULE OF ACTIVITIES (SoA)" the investigator (or subinvestigator) will record the time to alleviation of spasticity reported by subjects. The investigator shall ask the subject whether the product was effective on the spasticity, and if the subject's response to the question is positive, ask him/her "how many days did it take for the therapeutic effect to appear after the current dose?" and record the number of days.

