Exploratory	
Time to patient-reported onset of spasticity symptom relief will be evaluated for subjects who reported alleviation of spasticity at in 2 weeks postdose. The number of days from dose to the alleviation of spasticity will be summarized for each treatment group.
 
Clinical Global Impression of Change (CGI) assessed by an investigator, CGI assessed by a patient, and Patient-reported benefit of injection will be summarized for each treatment group. Missing values will not be complemented.
 
Other details will be specified in the statistical analysis plan.

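### Time to symptom relief is summarised only among subjects who report relief by Week 2, so the by-group summary is not a randomised comparison and may understate a dose difference

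*Protocol*

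**What the plan says.** The protocol text considered is the current one (Amendment 2).

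- **Analysis set.** Section 10.3.1, exploratory endpoints: "Time to patient-reported onset of spasticity symptom relief will be evaluated for subjects who reported alleviation of spasticity at in 2 weeks postdose".
- **Summary.** The next sentence reads: "The number of days from dose to the alleviation of spasticity will be summarized for each treatment group".
- **Collection.** Section 9.1.1.6 asks each subject at Visit 2 whether the product worked on the spasticity. The onset day is requested only "if the subject's response to the question is positive, ask him/her" how many days it took. The Schedule of Activities lists this item at V2 only, at Week 2 with a window of ±4 days.
- **General rule.** Section 10.3.1 opens with: "All of the efficacy analyses will be performed on the ITT population separately for the blinded period and the open-label period". It also says: "This study is not intended to verify a statistical hypothesis; thus, there will be no statistical test".
- **Purpose.** Section 4 lists the endpoint under an exploratory objective that includes comparing 400 units with 240 units.
- **Deferred.** The exploratory row ends: "Other details will be specified in the statistical analysis plan".

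The protocol does not say how subjects without relief at Visit 2 enter this analysis.

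**The concern.** Whether a subject reports relief by Week 2 is itself an effect of treatment. Selecting on it removes the protection of randomisation: the two sets compared are the early relievers of each arm, and these can differ in size and in kind.

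The selection also discards information. A subject who answers no at Visit 2 has an onset time known to exceed the time to that visit. That is a censored observation, and the protocol drops it. With all remaining times limited to about two weeks, the group summaries are pulled towards each other. An arm in which relief is slower or rarer can then look almost as fast as the other.

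The set also departs from the ITT rule at the head of the same section. Where that section wants another denominator, for the open-label responder rates, it says so explicitly; here it does not. At stake is whether the endpoint can answer the question Section 4 asks of it.

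**Working it through.** **The plan's own figures.** The protocol gives none for this endpoint. The sample-size figures in Section 10.1 concern the Week 6 elbow responder rate and do not bear on it.

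**Inputs.** The cut-off is T = 14 days (nominal Visit 2; the window makes it about Day 10 to 18). The relief rates by Day 14 are an assumption: 70% (400 units) versus 50% (240 units). They are borrowed from the Week 6 rates in Section 10.1 purely for illustration. With 60 subjects per arm, 42 and 30 would contribute.

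**Formulas, exponential onset.** For proportion p relieved by T:

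- rate λ = −ln(1 − p)/T
- all subjects: median = ln 2/λ; restricted mean to Day 14 = p/λ
- relievers only: mean = 1/λ − T(1 − p)/p; median = −ln(1 − p/2)/λ

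**Numbers.** λ = 1.2040/14 = 0.0860 per day for 400 units and 0.6931/14 = 0.0495 for 240 units.

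| Summary | 400 units | 240 units | Difference |
|---|---|---|---|
| All subjects, proportion relieved | 70% | 50% | 20 points |
| All subjects, median (days) | 8.1 | 14.0 | 5.9 |
| All subjects, restricted mean (days) | 8.1 | 10.1 | 2.0 |
| Relievers only, median (days) | 5.0 | 5.8 | 0.8 |
| Relievers only, mean (days) | 5.6 | 6.2 | 0.6 |

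From unrounded values, the relievers-only summaries keep 13% of the median difference and 29% of the restricted-mean difference.

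The mechanism shows in the identity: restricted mean = p × (mean among relievers) + (1 − p) × 14. For 400 units this is 0.7 × 5.63 + 0.3 × 14 = 8.1, and for 240 units 0.5 × 6.20 + 0.5 × 14 = 10.1. The (1 − p) × 14 term differs by 7.0 − 4.2 = 2.8 days between arms, and the relievers-only summary omits it.

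**Sensitivity to the assumed model.** Share of the all-subjects difference that survives:

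| Onset model | Relieved by Day 14 | Mean vs restricted mean | Median |
|---|---|---|---|
| Dose changes only the proportion relieved, not timing among relievers | any | 0% | 0% |
| Weibull, shape 0.7 to 3 | 50% vs 30% | 20% to 29% | 3% to 10% |
| Weibull, shape 0.7 to 3 | 70% vs 50% | 26% to 36% | 10% to 21% |
| Weibull, shape 0.7 to 3 | 95% vs 85% | 48% to 62% | 53% to 63% |
| Lognormal, medians 10 vs 15 days, log-SD 0.8 | 66% vs 47% | – | 26% (1.31 of 5.0 days) |
| Lognormal, medians 3 vs 6 days, log-SD 0.3 | about 100% in both | – | about 100% (2.99 of 3.0 days) |

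The loss is large when many subjects are unrelieved at Week 2 and vanishes when almost none are.

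**The case against.** The endpoint is one of several exploratory items. It is purely descriptive, no test is planned, and no success criterion rests on it. If n is printed beside the days summary, a contrast such as 42 versus 30 subjects would show that relief was rarer in one arm. Patient-rated CGI is collected from everyone at Visit 2 and summarised by group, so a difference in early perceived response would probably appear there too. The statistical analysis plan may add detail. All of this stands, and it limits the consequences.

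It does not remove the point. Section 10.3.1 itself fixes both the set and the summary and defers only the remaining details, so this is a stated choice rather than an omission. Printing n or reading CGI alongside does not make the days summary a comparison of randomised groups.

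Three limits on the remedy are also fair. Kaplan-Meier adds little beyond Visit 2, because follow-up for this item is one visit. A median will not be estimable in an arm with under 50% relief, so the proportion carries most of the information. The randomised-comparison argument does not extend to the open-label cycles, where both groups receive 400 units.

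A reader might infer that the selection hides almost all of any dose difference. The documents do not support that. An example with exponential onset and medians of 10 versus 20 days looks striking: 62% versus 38% relieved by Day 14, but 5.9 versus 6.4 days on average among relievers. That is one assumed model. Across plausible models the surviving share runs from 0% to about 100%, and the protocol supplies nothing to choose among them.

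**Conclusion.** The point holds as a minor one. The by-group summary of days to relief is conditioned on a post-randomisation outcome and cut off at about Day 10 to 18. It is therefore not a randomised comparison of 400 with 240 units and may understate or miss a difference in onset. It also sits badly with the ITT rule in the same section.

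The amount lost is not known. The 10% to 36% surviving at 70% versus 50% relieved rests on an assumed relief rate, Weibull onset and a common Day 14 cut-off. The primary endpoint and its analysis are unaffected.

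**What to change.** For the blinded period, amend the exploratory row of Section 10.3.1, or specify in the statistical analysis plan, as follows:

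1. In all ITT subjects, report per arm the proportion with relief by Visit 2, and the difference with a 95% CI.
2. Show a Kaplan-Meier (cumulative incidence) curve of time to reported relief, censoring subjects without relief at their actual Visit 2 date, since the window lets that date vary by up to 4 days either way.
3. State how ITT subjects with no Visit 2 answer are handled.
4. Keep days among reporters, with n per arm, as a supplement labelled as descriptive and conditional on relief.

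The open-label cycles can stay descriptive.

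The cost is wording and one extra table or figure. Section 9.1.1.6 already has every subject asked whether the product was effective, so no new visit or assessment is needed. The one thing to confirm is that the case report form keeps the negative answers and the visit date.
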